5.3.2. Fitbit

We will provide Fitbit (Inspire 3) that can alert participants with a vibration when they have been sitting for 60 minutes. Participants can select the days and the time ranges to receive the move alerts. Patients will be encouraged to review their daily summary before they go to bed.

The Fitbit is not intended to be used as a medical device. All participants will have the ability to monitor physical activity, sleep, and heart rate with the Fitbit. All data from the Fitbit will be continuously, streamed to the secured Fitbit servers. The study team member will assist participants in downloading the app and creating an account and will instruct them on how to use the device, with the official Fitbit user manual. When we create Fitbit accounts for research subjects, we do not use their real name or email address and default their account settings to the most privacy-protective option available.

Fitbit accounts require a unique email address for each user. To ensure participants' anonymity and privacy when creating Fitbit accounts, we will (1) set up anonymous Gmail accounts and (2) set up deidentified Fitbit accounts for the purpose of the study. This individualized email address will then be linked to a Fitbit account in which personal identifiers should not be used. Importantly, research staff and participants will be advised that the email and Fitbit accounts should be used strictly for the study's purpose. Moreover, account information will be stored in protected PI's computer within encrypted documents. Once the intervention is concluded, Fitbit data will not be collected. Also, Fitbit and Fitbit app will be reset for the participant to keep using the Fitbit after study completion.

5.3.3. Smart Water Bottle

We will provide a HidrateSpark water bottle, and the study team member will assist participants in downloading the app and creating an account. The study team member

will instruct participants on how to use the bottle, with the official user manual. The device alerts participants with a color change and message on the Fitbit to keep them hydrated. The device provides the daily water intake summary in the Fitbit app. We will advise participants to drink 4.5 – 6 bottles (500ml/bottle) of water per day based on current recommendations by the U.S. National Academies of Medicine.³⁵

The HidrateSpark accounts require a unique email address for each user and the same email which is used to Fitbit account will be used to the HidrateSpark app. The same rules will be applied to the HidrateSpark account, and the account information will be stored in protected PI's computer within encrypted documents.

Once the intervention is concluded, HidrateSpark data will not be collected. Also, HidrateSpark bottle and the app will be reset for the participant to keep using the bottle.

5.3.4. Weekly Text Message

Text messages will be provided to support and enhance the habit formation process. Text messaging has shown effectiveness in many exercise studies.³⁶⁻³⁸ There are three default text messages which will be sent and depending on study subject's preference, they will receive the text message up to one text message per day (a maximum of 10 text message a week). The first default text message will be sent on Thursday to provide feedback on their progress for the week. The second default text messages will be sent on Saturday morning to encourage them to sync their Fitbit to the Fitbit app. The third text messages will be sent on Monday morning to provide a weekly Fitbit summary and set next week's goal on reducing sedentary time. This Monday message will be structured by 1) positive reinforcement, 2) a weekly summary of sedentary time, steps counts and a suggestion for extra sitting breaks (data retrieved from Fitbit), 3) one tip from the TTT booklet, and 3) setting of next week's goal.

Participants will text back with a new goal. Examples of text messages are included in the appendix. Depending on the subject's preference, they will receive additional text messages which include positive reinforcement and encouragement. In addition to the weekly text messages, they will receive two monthly progress check up messages at the end of week 4 and week 8. These monthly text messages include their monthly sitting hours followed by restatement of overall goal. They will also get an introductory video explaining Fitbit app navigation and filling out the weekly goal sheet.

Below is the process of developing and providing text messages.

1. Creation of weekly text message template: [name] (Co-I), an expert in effective health communication, and the PI co-created the weekly message template with [name].
2. Fitbit data transfer: We will transfer the Fitbit data from the participants' Fitbit accounts to REDCap by developing our own data collection interface using Fitbit's Web Application Programming Interface (API). This platform provides secure data acquisition and management tools that facilitate remote data collection from Fitbit without the need for study participants to return the devices to researchers for data extraction.
3. Integration of Fitbit data into the text message template. The collected Fitbit data in the Redcap will be integrated into our weekly text message template.
4. Send text messages by using Twilio and Redcap. The customized text message will be sent using the Twilio plug-in for REDCap. Twilio module enables our study to make and receive SMS text messages, both to and from study participants. A REDCap and Twilio account are linked together. When a user indicates that an SMS (text) or a call should be sent to a cell phone, REDCap requests that action through Twilio. When a user responds, Twilio relays that information back to

Vanderbilt Diabetes and Research Training Center, P&F DK020593

REDCap. The data is stored in the REDCap database. Twilio does not store any data, nor does it keep a log of its actions.

5. Ask next week's goals via text message. This study uses survey function via SMS conversation to set a next week's sedentary hour and step counts goal. When participants take an SMS survey, questions are asked one at a time as an SMS text message conversation/thread. We will ask three questions (three SMS text messages). Participants may respond with any kind of alpha-numeric text for SMS survey. Only REDCap administrators are allowed to enable the Twilio option to initiate a survey as an SMS conversation. All messages and Fitbit data will be managed in REDCap.

5.4. Post-intervention visit

After 8 weeks, all participants will be invited to an in-person visit (post-intervention visit). During the visit, all the above parameters will be re-measured by the same trained research staff. The visit will take approximately 1 hour including completion of a series of questionnaires (which may be completed by the participants beforehand) and biometric assessments. All participants will wear the activPAL3 and the CGM for 7 days to examine their post-intervention activity and glycemic control. They will return the devices via pre-paid mail. All participants will receive \$50 for the post intervention visit, and an additional \$50 for mailing back the devices to the study team.

Therefore, total compensation would be \$150 for each participant. Also, all participants will be informed of their 24-hour glucose results, and activity patterns retrieved from the ActivPAL device. A subsample of participants from the intervention group will be invited to participate in a separate qualitative exit interview. The one-on-one exit interview will be conducted by the trained study team member during the visit. The interview will last 30 minutes, and each participant will be compensated with \$30 for completing this interview.

1. Questionnaires

Participants will answer the same questions about their demographics, socioeconomic characteristics, medical history and current medication, health behaviors, and patient-centered outcomes (e.g., fear of movement, confidence in reducing SB and increasing PA, habit strength for SB, quality of life, and depressive symptoms). Participants will have a choice to complete these questionnaires during the post-intervention visit in person or to receive paper copies of the questionnaires by mail. Printed copies will be identified by the participant's REDCap record ID number; there will be no additional identifying information on the printed questionnaires. If a participant chooses to receive the questionnaires by mail, he or she will be asked to complete them using a blue or black ink pen no sooner than 2 days prior to their scheduled post-intervention visit and will bring the completed surveys to their post-intervention visit. After the post-intervention visit is completed, the study team will enter their responses manually into REDCap and upload a scanned PDF version of the paper questionnaires to their REDCap record. Paper copies of the surveys will be kept in a locked cabinet in the study team's office at the Vanderbilt School of Nursing. In addition, participants will answer questions (Table 2) about feasibility and acceptability of the intervention. Level of satisfaction with the intervention will be assessed by using 23 items from the questionnaire developed by Lyons, Swartz, Lewis, Martinez and Jennings ³⁹ and Burner, Zhang, Terp, Bench, Lee, Lam, Torres, Menchine and Arora ⁴⁰. We will also use the 10-item of System Usability Scale⁵⁵ to assess usability. The scale is considered as "industry standard"

and provides a global measure of satisfaction ⁵⁶.

Table 2. Feasibility and Acceptability Assessment

Variables	Measures
Reach	(participants enrolled/participants screened and eligible) × 100
Retention	(participants completing post-intervention assessment/participants enrolled) × 100
Satisfaction	23 items from Lyons and Burner's questionnaires, System usability scale, Exit interviews (n=20)
Compliance	Number of days the Fitbit device was worn by week Number of days the Fitbit app was logged in by week

Number of text messages replied about the next week's goal

2. Biometric assessment

Participants will undergo the same physical examination (e.g., height, weight, blood pressure, hip circumference, waist circumference). The same protocol and instruments will be used.

3. activPAL data download

The 7 days of activPAL data will be downloaded and stored in the PI's computer.

4. Exit interview

A one-on-one interview will be conducted by the trained study team member during the post-intervention visit. The exit interview will be structured to capture feedback on the acceptability and satisfaction of the intervention, barriers and facilitators to SB reduction, and perceived health impacts of SB reduction. A semi-structured interview guide is attached in the appendix. The exit interview will be audio recorded by using a secure iPad and transcribed verbatim. The transcripts will be saved on the secure computer. The interview will take approximately 30 minutes.

1. To generate initial speech-to-text transcription of the mp4 audio file of the exit interview, trained study team members will utilize the transcription tool on a Microsoft Teams meeting. Alternatively, the Microsoft Word for OneDrive transcription tool will be used for recorded audio files. The mp4 file will be uploaded from the iPad to the Microsoft OneDrive Word application to begin transcription. These transcription methods have been approved and recommended by the VUMC Center for Technology Transfer and Commercialization. The transcript will be saved on the secured online VUSN server and only the study team will have access to the transcripts and audio recording files. De-identified audio files will be coded with four-digit numbers (ex. 0001) at the time of entry into the research study so that no direct identifiers appear on any samples or questionnaires. Audio files will be stored on a secure computer at Vanderbilt School of Nursing and password-protected, only accessible by the PI and/or her staff. No identifiable information will be stored on any mobile devices (laptops, USB keys, CDs, DVDs, etc.). The voice recording files that are saved under VUSN server will be permanently disposed 5 years after the study has been completed.

Table 3. Overview of Study Visits

	Screening	Baseline assessment 1	Baseline assessment 2	Intervention (Week 1 to Week 8)	Post-intervention assessment (after Week 8)	Exit interview (after Week 8)
Related personnel	Research staff	Research staff	Research staff	Research staff or PI	Study staff member	Research staff
Delivery methods	Phone or in-person	In-person	In-person	In-person for only initial session	In-person	In-person
Activity	Screening eligibility	Consenting, Support for completing questionnaires, distributing activPAL device and CGM	Biometric assessment, activPAL and CGM data download	Initial goal setting session, Activity tracker distribution, weekly text message	Support for completing questionnaires, Biometric assessment, Distributing activPAL and CGM	Structured one-on-one interview

Length of time needed	10 minutes	1hour	40minutes	Initial session: 1hour Weekly text message: 5-10minutes	1hour	30minutes
-----------------------	------------	-------	-----------	---	-------	-----------

6.0 Reporting of Adverse Events or Unanticipated Problems involving Risk to Participants or Others

Consent

For the pre-screening activity, potential participants recruited from the email distribution list or ResearchMatch will sign an e-consent in REDCap. Participants will be given information about what questions we will ask. There are no benefits or side effects related to this prescreening activity. Once they meet all the eligibility criteria, they will be invited for the in-person baseline visit. At the visit, participants are given as much time as they would like to consider participation from the initial invitation to participate until they sign the “main” consent form. Participants are encouraged to ask as many questions as possible and reminded that participation is completely voluntary and will not affect their medical rights. They are also told that they have the option to discontinue participation at any time for any reason.

Finger Prick Blood Test

Risks associated with the finger prick include: temporary discomfort from the needle prick, bruising, and rarely (<1%) infection. These risks will be minimized by using a sterile technique and applying sustained pressure to the site.

ActivPAL

The activPAL activity tracker is a safe, non-invasive method to capture information about activity cycles. Participation in this study requires that participants wear an activPAL tracker taped (using Tegaderm adhesive dressing) to the front of the right thigh during waking hours for a minimum of 7 consecutive days (baseline and follow-up). The Tegaderm adhesive dressing used to apply the activPAL devices are hypoallergenic and consist of a dual layer hydrogel that does not pull at the skin or hair. There are few risks associated with wearing the activPAL device and include slight discomfort, such as light pressure from the activPAL or irritation from the waterproof dressing.

Continuous Glucose Monitor

The FreeStyle Libre Pro Flash Glucose Monitoring System is an FDA-approved, professional continuous glucose monitoring device indicated for detecting trends and tracking patterns in persons (age 18 and older) with diabetes. After application of the sensor, only a thin, flexible filament will remain under the skin and the sensor is held in place by an adhesive. The following are possible adverse effects of inserting a sensor and wearing the adhesive patch: local erythema (redness), local infection, inflammation, pain or discomfort, bleeding at the glucose sensor insertion site, bruising, itching, scarring or skin discoloration, and adhesive irritation. There is a remote risk of sensor or needle fracture during insertion, wear or removal, with fragments retained under the skin.

Fitbit

Vanderbilt Diabetes and Research Training Center, P&F DK020593

Participants will wear an additional wrist-worn activity tracker for 8 weeks during waking

hours. There are few risks associated with wearing the device and include slight discomfort, such as light pressure from the wristband or irritation from wearing a damp band after showering or swimming. There is a possible risk of confidentiality loss. To reduce the risk, we will create an anonymous email account for the Fitbit app. All identifiable data will be kept on password-protected computer systems in a locked office.

Smart Water bottle

Participants will use the smart water bottle to increase the frequency of standing and moving by frequently going to the restroom and kitchen for refills. There is no risk associated with using the smart water bottle. To reduce the possible risk of confidentiality loss, we will create an anonymous email account for the HidraSpark app. All identifiable data will be kept on password-protected computer systems in a locked office.

8-Week Sedentary Behavior Intervention

Participants will gradually decrease their sedentary behavior and replace the sedentary behavior with a short period of light intensity physical activity such as 2 to 3 minutes of standing or walking over 8 weeks. The risk of falling or injury is the same as would be associated with day-to-day activity. Study staff members will instruct participants to make sure there are no hazards within the walking path and surrounding area.

Suicidal ideation or severe distress

Research has confirmed that simply asking a participant about whether they have thoughts of suicide is not a likely trigger of such an event⁴¹. It is usually only when the person reports ideation as well as an intent, plan, and/or means to commit suicide that risk for immediate suicide is considered to be more acute.

If a participant reports severe distress or suicidal ideation during the survey administration (Baseline visit 2 or Post-intervention visit), the research staff will immediately notify the PI. The PI will provide the participant with help to get treatment. This may include:

- working with the participant to contact his/her doctor,
- contact a trusted family member, or a therapist to discuss his/her thoughts,
- or work with the participant on a plan that may include getting him/her to a hospital for safety.

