5.1. Baseline visit 1: Initial contact, screening, and consent

Interested respondents will be screened by a trained research staff over the phone or in-

person, depending on the recruitment methods. For this research, no aspect of the participant's diabetes treatment regimen will be modified.

Those who are eligible for the study will be invited to the in-person visit. The first visit (i.e. Baseline visit 1) will be conducted at VUSN (Vanderbilt School of Nursing)'s lab at Wesley building.

At the Baseline visit 1, the trained research staff will ask the individual what their most recent blood glucose level was. If their reported glucose levels are between 80-300, they will complete the informed consent with assistance from the trained research staff.

Those who are consented will participate in 1) completing survey questionnaires (30minutes), 2) biometric assessments 3) brief instruction regarding the wear of activPAL and continuous glucose monitoring (CGM) devices (30 minutes), and 4) start to wear two devices for 7 days. The activPAL3 device (PAL Technologies Ltd., Scotland, UK) will be worn on the thigh and a CGM (Abbott FreeStyle Libre) will be attached to the upper arm. The research staff will provide 1) a copy of the informed consent form; 2) instructions with photos and 5 waterproof dressings (Tegaderm) for attaching the activPAL on the thigh; 3) information about the CGM; and 4) daily sleep diary and wear log for 7 days. Participants will receive \$25 for baseline visit 1.

1. Questionnaires

Participants will be given an iPad to answer questions about their demographics, socioeconomic characteristics, and a series of questionnaires detailed below. All responses will be recorded in REDCap.

- a) **Demographics:** demographics and socio-economic status will be self-reported by the patients.
- b) **Health behavior:** Questions about their tobacco use, alcohol intake, physical

activity (measured using the 16-item Global physical activity questionnaire²¹), sedentary behavior (measured using 11-item Weekly sitting inventory²²), and diet (measured using the 16-item Rapid Eating and Activity Assessment for Participants Short Version (REAP-S)²³, sleep quality (measured using the 10-item Pittsburgh sleep quality index²⁴) will be answered with the assistance of the study team member.

c) **Confidence in reducing SB and increasing PA:** Confidence in reducing SB and increasing physical activity will be measured using 12 items from the Self-

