Efficacy Questionnaire for Physical Activity and Sedentary Behavior (Cronbach's alpha = 0.79).²⁵

- d) **Habit strength for SB:** Habit strength for SB will be assessed by using a validated measure, Self-Report Habit Index (Cronbach's alpha = 0.91).²⁶ This 7-item index was adapted to sedentary breaks (standing/walking) to assess the degree to which sedentary breaks become habitual.
- e) **Quality of life:** Quality of life will be measured by using the 12-item Short Form Health Survey (SF-12). The SF-12 is well-validated in T2D patients²⁷ and provides physical and mental health scores.²⁸
- f) **Medical history and current medication:** Medical history and current medication will be self-reported by the patients.
- g) **Depressive symptoms:** Depressive symptoms will be measured by using Patients Health Questionnaire 9 (PHQ-9)²⁹.
- h) **Diabetes self-management:** Self-efficacy of diabetes self-management will be measured by the Perceived Diabetes Self-Management Scale³⁰.

2. Biometric assessments

Participants will undergo a basic physical examination (e.g., height, weight, blood pressure, hip circumference, waist circumference).

- a) **Anthropometrics:** Height, weight, and waist and hip circumferences will be measured using a validated stadiometer, digital scale, and flexible tape measure, respectively. All measurements will be recorded to the nearest 0.1 cm and 0.1 kg.
- b) **Blood pressure:** Blood pressure will be measured using an automated and validated BP monitor. In a private room, participants will be seated comfortably for 5 minutes with feet flat on the ground prior to measurements.³² The device will take three readings at 2-minute intervals and the mean of three BP readings will be recorded.³²
- c) **Random glucose via finger prick:** The trained research staff will conduct a finger prick and one drop of blood will be obtained on a glucometer. The glucometer will be used to test their random glucose. Participants will NOT be required to fast overnight prior to the study visit. If the random glucose >300, the PI will be immediately informed and the participant will be withdrawn per the protocol (see section 7).

3. ActivPAL

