5.2.1. Device removal

The in-person baseline visit 2 will take place at the VUSN Clinic in the Wesley building. Participants will return the activPAL and the continuous glucose monitoring devices at Baseline visit 2. The trained research staff will assist the participant in removing the two devices as needed, and then download the data from the activPAL and CGM devices. Baseline visit 2 will last approximately 1 hour and 30 minutes. Participants will receive \$25 for baseline visit 2.

1. ActivPAL data download

The 7 days of activPAL data will be downloaded and stored in the secured PI's computer. The variables of interest from the activPAL data are listed below:

- a) **Sedentary behavior:** SB will be objectively measured as time spent sedentary (sitting or lying, minutes/day) and number of prolonged sedentary bouts (>30 minutes and >60 minutes) using the activPAL3. ActivPAL data will be downloaded and processed using activPAL software.
- b) **Physical activity:** Time spent standing and walking (stepping), number of sitting-to-standing transitions, and daily step counts will be measured using the activPAL.

2. Continuous glucose monitoring data download

The 7 days of CGM data will be downloaded via Libreview and stored in the PI's computer. The variables of interest from the CGM data are listed below:

- a) The 24-hour glucose control: the 24-hour glucose control will be evaluated by mean 24-hour glucose levels and numbers of events and time in hypoglycaemia (glucose < 3.9 mmol/l), euglycaemia (glucose 3.9–7.8 mmol/l), hyperglycaemia (glucose > 7.8 mmol/l) and above target (glucose > 9 mmol/l).

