5.3.1. Instructional/goal setting session

The study team member will provide an orientation at the baseline visit 2. The study team member will review the activPAL data and identify targetable prolonged SB bouts. The study team member and the participant will set two goals: 1) a SB reduction goal will be set as reducing daily sedentary time gradually until they reach the goal of ≥ 120 minutes SB reduction; and 2) a sedentary break goal will be set as 3 minutes of standing/walking every 1 hour and then increasing its duration to 5 minutes and its frequency to every 30 minutes. These goals were feasible in stroke patients and T2D patients.^{16,33} The participant will enter the goal into the Fitbit for self-monitoring and fill out the first worksheet in the Ten Top Tips (TTT). The TTT is a booklet developed from the Habit Formation Theory and includes 10 tips to add SB breaks into their daily routine.³⁴ The ten tips are modified to eight in our study. See Appendix for the TTT and worksheet. This goal session will last 1 hour.

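### Section 6.0 attaches the suicidal-ideation procedure to Baseline visit 2, but the baseline survey is given at Baseline visit 1, and the plan does not say when staff see a written positive answer

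*Combined protocol and SAP*

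**What the plan says.** Section 6.0, under the sub-heading on suicidal ideation or severe distress, first argues that "simply asking a participant about whether they have thoughts of suicide is not a likely trigger" of suicide. It then gives the response: "If a participant reports severe distress or suicidal ideation during the survey administration (Baseline visit 2 or Post-intervention visit", staff tell the principal investigator at once, and the investigator helps the participant get treatment.

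Section 5.1 puts the baseline survey at Baseline visit 1: "Those who are consented will participate in 1) completing survey questionnaires (30minutes". On the method it says "Participants will be given an iPad to answer questions about their demographics, socioeconomic characteristics, and a series of questionnaires detailed below", with all answers stored in REDCap. Item g of that list reads "Depressive symptoms will be measured by using Patients Health Questionnaire 9 (PHQ-9". Staff help is written into item b, the health-behaviour questions, which "will be answered with the assistance of the study team member"; item g has no such wording. Table 3 lists general support with questionnaires under Baseline assessment 1 and under the post-intervention assessment.

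For the second baseline visit, Section 5.2.1 says "Participants will return the activPAL and the continuous glucose monitoring devices at Baseline visit 2" and Section 5.3.1 says "The study team member will provide an orientation at the baseline visit 2". Table 3 gives it biometric assessment and data download. None of the three lists a questionnaire.

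Section 5.4 asks about depressive symptoms again after the intervention. Participants may answer in person or on mailed paper forms, filled in at most 2 days before the visit and brought to it. Staff key the paper answers into REDCap, and upload a scan, once the visit is over.

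**The concern.** Staff carry out this instruction under time pressure, so it should match the visit schedule. It names a baseline visit at which the survey is not given. That visit comes after 7 days of device wear, so about a week after the participant answered.

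The second gap matters more. The procedure starts with a report, and the plan describes no point at which staff look at what the participant entered on the iPad or wrote on paper. A participant who tells a staff member is covered at either survey visit. A participant who only marks an answer is covered if someone reads it in time, and the plan does not say who does so or when. For a form completed at home, following the written steps and no others would allow the answer to be first seen after the participant has gone. That would defeat the plan's own requirement to notify the investigator at once.

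**Working it through.** The plan gives no figure to reproduce. The check compares the sections, then counts the forms affected.

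**Visit and route of the answer**

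| Occasion | Where the survey is placed | Visit named in Section 6.0 | Stated route of the answer | Stated step for staff to read it before departure |
|---|---|---|---|---|
| Baseline | Baseline visit 1 (Section 5.1; Table 3) | Baseline visit 2 | iPad to REDCap | None |
| Post-intervention, in person | Post-intervention visit (Section 5.4; Table 3) | Post-intervention visit | Completed at the visit | None |
| Post-intervention, mailed paper | At home, up to 2 days before; brought to the visit (Section 5.4) | Post-intervention visit | Paper, then REDCap entry after the visit | None |

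The text and Table 3 agree with each other and disagree with Section 6.0 on the baseline visit. No score threshold, REDCap alert or hand-in check is stated for any of the three routes.

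**Is the ideation question in this survey?** The PHQ-9 items are not printed. Section 6.0 discusses asking participants about suicidal thoughts and expects ideation to be reported during the survey. The PHQ-9 is the only depressive-symptom measure in the list. The inference is reasonable, but it is an inference.

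**Forms still to come**, from Section 8.0 (16 recruited, 3 withdrawn, 5 in the intervention group and 8 in control, a total of 40 planned, 15% attrition):

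- Baseline forms: 40 − 16 = 24.
- Post-intervention forms from those 24: 24 × (1 − 0.15) = 20.4, about 20.
- Participants already in the study: 16 − 3 = 13, which matches 5 + 8. How many had already given a post-intervention form is not stated, so 0 to 13 remain.
- Total: 24 + 20 + 0 = 44, up to 24 + 20 + 13 = 57.
- Forms that could be completed at home: post-intervention only, from 0 to 20 + 13 = 33. The share choosing paper is not stated.

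These counts show how many forms a checking step would cover. They do not estimate how many positive answers would occur or go unseen; the documents give no rate for either.

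**The case against.** The strongest reply is that the wrong visit label changes little by itself. The operative condition is a report made while the survey is being given, and staff running the survey at Baseline visit 1 would probably follow the paragraph whatever its parenthesis says. That stands: taken alone, the label is a one-word correction.

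The reply goes on that a report need not be spoken. Section 6.0 links it to the survey and to asking about suicidal thoughts, so a positive survey answer can already be read as a report, and a duty to notify at once presupposes that somebody looks. Table 3's support with questionnaires does not exclude the PHQ-9. This is also fair, and it narrows the point to how and when staff see the answer. General support does not require anyone to read a particular item, so that question stays open.

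A reader might infer that staff are meant to leave paper forms unread until the visit is over. The documents do not support this. Section 5.4 times the REDCap entry and scanning, and does not bar anyone from reading a form when it is handed in. The plan is silent here; it does not give a contrary instruction.

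An appendix might also cover the step. The appendices are not in the text available, but neither the questionnaire sections nor Section 6.0 refers to one for this purpose.

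**Conclusion.** The point holds in two parts. First, Section 6.0 names the wrong baseline visit; Section 5.1 and Table 3 settle this. Second, no section says when staff see a written positive answer, at baseline or after the intervention. The gap is clearest for forms completed at home. The second part carries the weight, and it should be fixed.

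The size is 44 to 57 forms still to come at the date in Section 8.0, of which 0 to 33 could be done at home. This assumes that all 24 new participants complete the baseline survey and that the 15% attrition applies to them. The point also rests on the inference that the PHQ-9 carries the ideation question.

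A reader might conclude that positive answers will be missed, or that ideation reported at Baseline visit 1 would go unanswered. The documents show neither: staff are present at both survey visits and can act on what they hear or read. Confidence is high that the label is wrong and that the step is not written down. Nothing can be said about how often an answer would go unseen. Sample size, outcomes and analysis are not affected.

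**What to change.** In Section 6.0:

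1. Replace Baseline visit 2 with Baseline visit 1 and keep the post-intervention visit.
2. State that a positive written answer counts as a report and triggers the same immediate notice to the principal investigator as a spoken one.
3. Require staff to check the ideation item before the participant leaves: on the REDCap entry at Baseline visit 1, and on the REDCap entry or the paper form at hand-in at the post-intervention visit. Repeat the hand-in check in Section 5.4, next to the text on mailed forms.

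The cost is a wording amendment and, at an assumed 1 minute per form, 44 to 57 minutes of staff time over the remaining forms.

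A separate item for the clinical lead, not part of this point or its weight: the hypoglycaemia protocol in Section 7.0 offers 15 mg of glucose in tablet form as an alternative to 60 ml of juice. The two would match only if juice held 0.015 g ÷ 0.060 L = 0.25 g of sugar per litre, so a unit error is likely. The documents do not show which dose was intended.
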